STATISTICAL ANALYSIS PLAN

March 26, 2019

NCT# 02772432

Development of a Resiliency Training Program for Parents of Children With Specific

Learning Disabilities

Randomization

We asked participants for their daytime or evening time preferences prior to randomizing them to the intervention or control from November 2016 to September 2017, balancing for group size. Participants were randomized using a random plan generator, with 1:1 randomization.

Statistical Analyses

To assess study feasibility, we assessed enrollment, intervention session attendance (>6) and retention at time 2 (75% response; intervention group: end of treatment; wait-list control: 3-month post-enrollment) and time 3 (intervention group: 3-months post end-of treatment; wait-list control: end of treatment). Study completers and non-completers at time 2 were compared on baseline demographic characteristics using independent samples t-tests for continuous variables and Chi-square tests or Fisher's exact tests for categorical variables. To assess study acceptability, we reviewed participant self-report survey feedback (e.g., satisfaction with the number and length of intervention sessions, comfort level with group sessions, continued RR practice) and open-ended qualitative program feedback. To explore preliminary efficacy of the intervention to improve our proposed psychosocial outcomes, we first characterized the two randomized groups (intervention group and wait-list control) by baseline demographic factors and reviewed baseline psychosocial data for univariate distributions. We then used all available data to test between-group (intervention group versus wait-list control) differences in change scores from time 1 to time 2 (intervention group: end of treatment; wait-list control: 3-month post-enrollment) using independent samples t-tests. Using the intent-to-treat principle, we replicated the analysis using multiple imputation⁶⁶ (five imputed datasets) to address missingness at time 2.

We followed our main preliminary efficacy analyses with a series of paired samples t-tests using all available data, to further characterize results. First, we evaluated changes in scores from time 1 to time 2 within each randomized group. To further explore intervention efficacy, we evaluated the combined change from pre- to post-intervention across intervention group condition participants (using time 1 to time 2 data) and wait-list control participants (using time 2 to time 3 data). Finally, we explored potential maintenance of intervention benefits by evaluating change in scores from time 2 to time 3 within the intervention group only. Additionally, to support a future larger scale trial, including identification of a potential moderator of intervention effects, we explored whether greater parenting stress at baseline was associated with greater changes in our proposed psychosocial outcomes among participants (before treatment and end of treatment) using Pearson correlations.

Running head: A VIRTUAL INTERVENTION PROMOTING RESILIENCY FOR PARENTS OF CHILDREN WITH LAD Analyses were conducted using IBM SPSS version 23.

Running head: A VIRTUAL INTERVENTION PROMOTING RESILIENCY FOR PARENTS OF CHILDREN WITH LAD

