A total of approximately 70 participants will be recruited for this study. Both males and females from diverse racial and ethnic backgrounds will be recruited using IRB approved procedures. Potential participants will be recruited from our contacts in the community including other MGH

clinicians, as well as through local and national support groups and list serves using IRB approved recruitment materials. MGH child psychologists may also refer potentially eligible participants. In each case, interested participants will be directed to our pre-screen REDCap survey and will be given the option to contact the study staff to learn more about the study.

IV. SUBJECT ENROLLMENT

Methods of enrollment

Participants will contact the PI or study staff by telephone, email, or by completing our IRB approved pre-screen REDCap survey in response to advertisements. Subject will be contacted by phone, informed about the study and given a pre-screen REDCap to determine whether they meet inclusion/exclusion criteria (see the attached pre-screening questionnaire). Subjects may also be referred to the study. Subjects must respond “yes” to all inclusion criteria and “no” to all exclusion criteria to be eligible for the study. Eligible participants will be consented and will complete the baseline survey online into REDCap, a secure, web-based application designed to support data capture for research studies.

Randomization

After enrollment, participants will be randomized to the Immediate intervention group (IG) or Waitlist control group (WG). Randomization will be conducted using a random plan generator, with 1:1 randomization. The WG will begin their program approximately 3 months after the SMART-3RP group. For both groups, the intervention will last approximately 8 weeks, weekly with groups meeting once per week for approximately 1 hour.

Informed consent process

Eligible and interested participants will be sent a consent form and scheduled for a phone consent. Informed consent and authorization will be obtained and documented through use of a written consent form approved by the Partners Human Research Committee (PHRC) and signed by the participant. The PI or qualified study staff will complete informed consent procedures.

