Acceptability will be assessed using a Participant Feedback questionnaire (See Feedback questionnaire attached).

2) Is the virtual SMART-3RP program effective for parents of children with learning disabilities?

a) Is there a significant difference in primary and secondary outcome measures between participants in the Immediate and Waitlist SMART-3RP groups at 3 mo. post enrollment?

We will use paired samples t-tests to compare within group differences on primary and secondary outcome measures from 3 mo. to baseline for the Immediate and Waitlist Groups. Primary outcome measures are the General Self-Efficacy Questionnaire (GSE), Current Experiences Scale (CES; from the Post Traumatic Growth Inventory), and the Visual Analogue 0-10 scales (VAS; measuring stress, distress, coping, and physical discomfort). Secondary outcome measures are: the Measure of Current Status-A (MOCS-A; to assess stress reactivity), Cognitive and Affective Mindfulness Scale-Revised (CAMS-R; to assess growth enhancement), and the Parental Stress Scale (PSS; to assess parental stress).

We will then use independent samples t-tests to compare the difference between the Immediate group's 3 months post enrollment and baseline assessment results with the

difference between the waitlist group's 3 months and baseline assessment results on primary and secondary outcome measures.

b) Among participants randomized to both conditions, will there be improvements in primary and secondary outcome measures from pre-post SMART-3RP (IG: assessments from baseline-3 mo.; WG: from 3-6 mo.)?

We will use paired samples t-tests to compare all primary and secondary assessments from pre-post SMART-3RP (for the IG, assessments are from baseline-3 mo.; for the WG, assessments are 3 mo. to 6 mo.).

c) Among the Immediate group only, will the changes from baseline to 3 months post enrollment (end of treatment) be sustained at 6 months post enrollment (3 months post treatment)?

We will use paired samples t-test to assess within-group differences in long-term outcomes. We will compare measures at the 6 months assessment to measures at the 3 months assessment for the Immediate group.

3) Will the virtual delivery SMART-3RP be effective in reducing participants' stress levels, measured by hair cortisol?

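### Daytime or evening preference was recorded before randomization but is left out of the between-arm tests; adjusting for it is a cheap precision gain, and the SAP should say whether it drove allocation

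*SAP*

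**What the plan says.** **Allocation.** The SAP's Randomization section opens: "We asked participants for their daytime or evening time preferences prior to randomizing them to the intervention or control", and the sentence continues "from November 2016 to September 2017, balancing for group size". It then says: "Participants were randomized using a random plan generator, with 1:1 randomization". No strata or blocks are named, and the size being balanced is not defined. The protocol (section IV, Randomization) has only the generator: "Randomization will be conducted using a random plan generator, with 1:1 randomization". It mentions neither a time preference nor any balancing.

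**Analysis.** The SAP's main efficacy comparison (Statistical Analyses) tests between-arm "differences in change scores from time 1 to time 2" with independent samples t-tests. For missing time 2 data, "we replicated the analysis using multiple imputation" with five imputed datasets; the variables in the imputation model are not listed. The protocol (section VI, question 2a) planned the same unadjusted comparison: "We will then use independent samples t-tests to compare the difference between the Immediate group's 3 months post enrollment and baseline assessment results". Neither document names a covariate for this comparison.

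**Size.** Protocol section III, Recruitment: "A total of approximately 70 participants will be recruited for this study". No significance level, power, effect size or standard deviation accompanies that number.

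**The concern.** When arms are forced to equal numbers within levels of a factor, differences between those levels cancel out of the arm contrast. A two-sample t-test does not know this. It leaves the between-level variation in its error term, so the reported standard error exceeds the real one whenever the factor predicts the outcome being compared. The usual remedy is to put the allocation factor in the model.

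The SAP presents slot preference as part of how parents were allocated, and the intervention is delivered in live weekly groups, so filling daytime and evening slots evenly by arm is a natural reading. At stake would be some lost power and over-wide intervals in a trial of about 70 parents. A false positive is not at stake, because any error from this source is conservative.

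There is a weaker version that does not depend on how allocation was done. Preference is a recorded pre-randomization variable, so adjusting for it is legitimate under either reading and can sharpen the estimate if it is related to change.

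**Working it through.** **Inputs from the documents.** About 70 parents at 1:1, so 35 per arm. The SAP's time 2 retention criterion is 75%: 0.75 × 70 = 52.5, about 52 analysed, or 26 per arm. The outcome is change from time 1 to time 2.

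**Inputs assumed, because the documents give none.** Two-sided 5% level; change-score SD of 1; half of parents preferring daytime; R², the share of change-score variance explained by preference, at 0.05, 0.10 and 0.20; and a difference of 0.67 SD for power, which 35 per arm detects with 80% power. The target of about 70 has no derivation, so there is no planned figure to reproduce.

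**Case A: arms balanced within preference.**

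- Reported SE / true SE of the t-test = 1/√(1−R²).
- True type I error = 2 × [1 − Φ(1.96/√(1−R²))].
- With δ = 0.67/√(2/35) = 2.80, unadjusted power = Φ((δ − 1.96)/√(1−R²)) and adjusted power = Φ(δ/√(1−R²) − 1.96).

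| R² | SE ratio | Type I error | Power, unadjusted | Power, adjusted |
|---|---|---|---|---|
| 0 | 1.000 | 0.050 | 80.0% | 80.0% |
| 0.05 | 1/√0.95 = 1.026 | 0.044 | 80.6% | 82.0% |
| 0.10 | 1/√0.90 = 1.054 | 0.039 | 81.3% | 84.0% |
| 0.20 | 1/√0.80 = 1.118 | 0.028 | 82.7% | 88.0% |

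Simulation agrees (10,000 null trials per setting). At N = 70 the SE ratios were 1.029, 1.062 and 1.110, with type I error 0.042, 0.036 and 0.031. At N = 52 they were 1.040, 1.069 and 1.117, with type I error 0.041, 0.036 and 0.028.

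**Case B: 1:1 overall, not stratified by preference.** The same simulation at N = 70:

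| R² | Reported/true SE of t-test | Type I error of t-test | Mean SE, unadjusted → adjusted |
|---|---|---|---|
| 0 | 1.007 | 0.047 | 0.238 → 0.240 |
| 0.05 | 0.997 | 0.051 | 0.238 → 0.233 |
| 0.10 | 1.001 | 0.048 | 0.238 → 0.228 |
| 0.20 | 0.980 | 0.054 | 0.239 → 0.215 |

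Here the t-test's standard error is correct, and adjustment only narrows it. The R² = 0 row shows the price when preference is irrelevant: the mean SE rises from 0.2383 to 0.2400, under 1%.

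**The opposing effect of group delivery.** At time 2 only the immediate arm has attended group sessions. With session groups of size m and intraclass correlation ICC, the treated arm's variance is multiplied by DE = 1 + (m−1)ICC, and true SE / t-test SE = √((1+DE)/2). Both m and ICC are assumed:

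- m = 6, ICC = 0.02: DE = 1.10, ratio √1.05 = 1.025.
- m = 8, ICC = 0.05: DE = 1.35, ratio √1.175 = 1.084.
- m = 10, ICC = 0.10: DE = 1.90, ratio √1.45 = 1.204.

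The t-test's standard error would thus be too narrow, with the true one 2.5% to 20% larger. That is the same order as the Case A effect, and opposite in sign.

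**The case against.** The strongest case against is that stratification is nowhere stated. The SAP mostly uses the word group to mean a randomized arm, so balancing for group size may mean no more than equal arm sizes, which does no harm to a t-test. It could also mean the size of session groups. Asking parents when they are free before assigning them to live weekly sessions is compatible with scheduling alone, and the protocol describes a plain 1:1 plan. This stands: Case A is possible but not documented.

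A reader might infer that the standard errors are too wide simply because preference is prognostic. That does not follow. Case B shows a prognostic factor leaving the t-test valid when allocation was not balanced on it. Preference must also predict *change*, not just the level of the outcome. The Background in protocol section I links caring for a child with special needs to non-employment and financial stress, but says nothing about time-of-day availability or who improves.

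A reader might also infer that the reported intervals are over-wide overall. The documents do not support that either, since unmodelled clustering by session group pulls the other way and could cancel or exceed the effect.

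Finally, the analysis is labelled preliminary, the error is conservative, and the SAP is dated March 2019 and written in the past tense, so an adjusted model is now a late addition. These points lower the severity and govern how the result is labelled. They do not remove the case for adding the term, which is valid under either allocation and almost free.

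**Conclusion.** Upheld as a low-severity precision and reporting point, not as a demonstrated error. What is certain is that preference was obtained before allocation, that no between-arm comparison uses it, and that the allocation wording is ambiguous and fuller than the protocol's.

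The rest is conditional. If arms were balanced within preference and preference predicts change, the t-test's standard error is too wide by about 3%, 5% or 12% at R² of 0.05, 0.10 or 0.20, and adjustment adds about 1, 3 or 5 points of power at the assumed 0.67 SD with all 70 analysed. If allocation was not stratified, the test is sound and adjustment lowers the mean standard error from 0.238 to 0.228 at R² = 0.10. If R² is near zero there is no material gain. R², the slot split and the effect size are all assumptions. No conclusion follows about the direction of error in the overall standard error.

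**What to change.** 1. State in the SAP what the group-size balancing referred to (arms, session groups or time slots) and whether preference was a stratification factor, and reconcile this with the protocol's Randomization section.
2. Report each between-arm comparison from a linear model for change with arm plus daytime/evening preference. Show the planned unadjusted t-test alongside, and label the adjusted model as added to the plan.
3. Include preference in the imputation model and list that model's variables.

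The cost is one extra term in SPSS, one degree of freedom and a few sentences. The preference was asked for before randomization, so no new data are needed. This change does not deal with clustering by session group, which is a separate matter.

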Specific Aim 1 (Phase II): Informed by Phase I findings, (approved in a previous IRB protocol #2016P000423), we aim to develop and determine the feasibility (by assessing the number of sessions attended and adherence to Relaxation Response practice) and acceptability (assessed using the Participant Feedback Survey) of an 8-session Relaxation Response Resiliency (SMART-3RP) program for parents of children with learning disabilities.

Hypothesis: The SMART-3RP virtual delivery will be feasible to implement and acceptable to parents of children with learning disabilities.

Primary Aim 2 (Phase III): To test the effectiveness of a pilot waitlist controlled trial on improving resiliency, as measured using the General Self-Efficacy Questionnaire, Current Experiences Scale, and the Visual Analogue 0-10 scales (including stress, distress, coping, and physical discomfort), and on improving stress reactivity (as measured by the Measure of Current Status-A), growth enhancement (as measured by the Cognitive and Affective Mindfulness Scale-Revised), and parental stress (as measured by the Parental Stress Scale). This will be assessed by comparing Baseline-3 mo. scores on primary and secondary outcome measures between the Immediate and Waitlist control groups.

Primary Hypothesis: Patients randomized to the Immediate group will report significantly greater scores on the primary outcomes (measures of resilience) and on the secondary outcomes (measures of stress reactivity, growth enhancement, and parental stress) at 3 mo. post enrollment.

Secondary Aims: Among participants randomized to both conditions, to investigate the extent of pre-post changes in primary and secondary outcomes (Immediate: assessments from baseline-3 mo.; Waitlist: from 3-6 mo.).

Secondary Hypothesis: Scores on primary and secondary outcome measures will improve from pre-post intervention.

Secondary Aim 2: Among immediate condition group only, to assess whether end-of-treatment (3 mo. post enrollment) improvements will be sustained at 6-mo. post enrollment.

Hypothesis: These end-of-treatment effects will show sustained improvement on primary and secondary outcome measures from 3 to 6-mo. Post enrollment.

Secondary Aim 3: To pilot test the end-of-treatment effects of the SMART-3RP on parents' stress levels using hair cortisol. A mixed effects models approach will be used to examine group

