In the SMART-3RP intervention, sessions focus on developing an understanding of stress physiology and the physiology of the relaxation response (RR), on developing a regular practice of eliciting the RR, and on learning cognitive behavioral and positive psychology/resilience skills. In addition to the weekly group sessions, participants will receive audio recorded guided meditations for independent relaxation practice. Participants are expected to practice eliciting the RR for approximately 20 minutes a day throughout the course of the study, using the audio recording provided and/or any other meditative or mind body techniques. Participants will complete a daily log reporting how often and by which methods they are practicing the RR. (Please see attached practice log).

Participants randomized to Immediate or Waitlist will participate in the SMART-3RP program. Participants in the Immediate arm will be encouraged to practice the skills taught in the program during the 3 month follow up period after completion of the 8 session SMART-3RP. Participants in the Waitlist arm will wait for approximately 3 months before beginning the SMART-3RP.

Participants in both groups will be given questionnaires at the same time points (baseline, 3 month post enrollment, and 6 month post enrollment). Study staff will email these questionnaires to the participants via the REDCap system. Participants who have not responded within two weeks of each time point will be contacted by telephone to ensure receipt of study data.

Figure 1 (below) illustrates the administration of questionnaires in both groups.

Figure 1. Study Design.

Baseline
T1

3 mo. Post
Enrollment
T2

6 mo. Post
Enrollment
T3

Remuneration

Participants will be given a \$20 gift certificate for completing 3 mo. survey and another \$20 gift certificate for completing the 6 mo. survey assessment.

VI. BIOSTATISTIC ANALYSIS

We plan to conduct a pilot trial of a virtual-based SMART-3RP intervention for parents of children with learning disabilities. Participants in this trial will be randomized to one of two groups: 1) Immediate SMART-3RP intervention, or 2) Waitlist control SMART-3RP group (starting approximately 3 months after enrollment).

The following questions will be assessed:

1) Is the virtual SMART-3RP feasible and acceptable for parents who have children with learning disabilities?

Feasibility will be assessed using attendance and homework completion (i.e. 6/8 sessions and homework completion).

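### The lead between-arm efficacy test is a t-test on change scores with no covariate; a baseline-adjusted estimate from the same data would generally be more precise

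*SAP*

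**What the plan says.** The SAP (Statistical Analyses) compares the arms on "differences in change scores from time 1 to time 2 (intervention group: end of treatment; wait-list control: 3-month post-enrollment) using independent samples t-tests", using all available data, and then repeats that analysis in five imputed datasets. Its next paragraph confirms the standing of the test: "We followed our main preliminary efficacy analyses with a series of paired samples t-tests using all available data".

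The protocol (Section VI, question 2a) plans the same thing: "We will then use independent samples t-tests to compare the difference between the Immediate" group's baseline to 3-month difference with that of the waitlist group. This comparison carries the Primary Hypothesis in Section II: "Patients randomized to the Immediate group will report significantly greater scores on the primary outcomes". Question 2a lists nine measures: GSE, CES, four VAS items, MOCS-A, CAMS-R and PSS.

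The covariate is already planned for everyone: "Eligible participants will be consented and will complete the baseline survey online into REDCap" (Section IV), and the same battery is repeated at 3 months (Section V). Yet neither document estimates a baseline slope in a psychosocial arm comparison. The SAP uses baseline psychosocial scores to look at distributions and to correlate parenting stress with later change. The mixed effects model in Section VI, question 3, is for hair cortisol only. Multiple imputation repeats the change-score comparison; it does not replace the estimator.

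**The concern.** A change score does use baseline, but it subtracts the whole baseline value whether or not follow-up tracks it one for one. When the within-arm slope of follow-up on baseline differs from 1, some baseline noise stays in the comparison. ANCOVA estimates the slope and removes it.

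Precision is scarce here. The protocol says "A total of approximately 70 participants will be recruited for this study", and the SAP's benchmark is "retention at time 2 (75% response". The interval for the arm effect on each outcome is then generally wider than the data require. Neither document states a power target or says these estimates will size a later trial, so what is at stake is precision and nothing more.

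**Working it through.** The plan gives no power, effect size, SD or derivation of its sample size, so there is no figure to reproduce.

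**Inputs from the documents**
- About 70 participants (Protocol, Section III, Recruitment), allocated 1:1 (Section IV).
- 75% response at time 2 (SAP). This is a benchmark, not a forecast.
- Per arm: 70 × 0.75 / 2 = 26.25, taken as n = 26; 35 with no loss.

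**Assumed, because the documents are silent**
- Correlation rho between baseline and time 2: 0.3, 0.5, 0.7, 0.9.
- Ratio k = baseline SD / follow-up SD: 0.8, 1.0, 1.25, with follow-up SD set to 1.
- Independent participants, complete data.

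**Formulas (variance per participant)**
- Change score: 1 + k² − 2·rho·k
- ANCOVA: 1 − rho²
- Difference: (k − rho)², which is never negative and is zero when k = rho, that is, when the true slope is 1.
- Cost of estimating the slope: multiply the ANCOVA variance by 1 + 1/(2n − 4) = 1 + 1/48 = 1.0208 at n = 26.
- SE = √(2 × variance / n). The t reference has 50 df for the change score and 49 for ANCOVA.

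**Worked case: k = 1, rho = 0.5, n = 26**
- Change score: variance 1 + 1 − 1 = 1.00; SE = √(2/26) = 0.277; 95% half-width 0.557.
- ANCOVA: variance 0.75; SE = √(2 × 0.75 × 1.0208 / 26) = 0.243; half-width 0.488.
- Variance ratio 0.75 × 1.0208 = 0.766, so the SE falls by 1 − √0.766 = 12.5%. To match, the change score would need 1/0.766 = 1.31 times as many participants.

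**SE reduction from ANCOVA at 26 per arm, after the slope cost**

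| k | rho 0.3 | rho 0.5 | rho 0.7 | rho 0.9 |
|---|---|---|---|---|
| 0.8 | 10.5% | 4.5% | −0.1% | 1.5% |
| 1.0 | 18.5% | 12.5% | 6.8% | 1.5% |
| 1.25 | 28.4% | 23.6% | 20.0% | 21.2% |

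At 35 per arm and k = 1.0: 18.8%, 12.7%, 7.1%, 1.8%.

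**95% CI half-width at 26 per arm, in follow-up SDs (change score / ANCOVA)**

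| k | rho 0.3 | rho 0.5 | rho 0.7 | rho 0.9 |
|---|---|---|---|---|
| 0.8 | 0.600 / 0.537 | 0.511 / 0.488 | 0.402 / 0.402 | 0.249 / 0.245 |
| 1.0 | 0.659 / 0.537 | 0.557 / 0.488 | 0.432 / 0.402 | 0.249 / 0.245 |
| 1.25 | 0.750 / 0.537 | 0.638 / 0.488 | 0.502 / 0.402 | 0.311 / 0.245 |

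**Worst case.** At k = rho the ANCOVA SE is √1.0208 = 1.010 times the change-score SE, and the half-width is 1.011 times as large. With equal SDs, ANCOVA loses only if rho exceeds about 0.96.

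**Simulation check.** With 20,000 trials in each of the 12 cells at 26 per arm, with complete and independent data, type I error was 0.047 to 0.053 for the change score and 0.048 to 0.052 for ANCOVA. Absolute bias was at most 0.005 SD for both. At k = 1.0 the empirical SE reductions were 18.6%, 12.5%, 6.8% and 1.5%, in line with the formulas.

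**The case against.** The strongest reply is that nothing here is invalid. Protocol and SAP agree on the test, it is unbiased under randomisation, and the stated setting is modest: "We plan to conduct a pilot trial of a virtual-based SMART-3RP intervention for parents of children with learning disabilities". No decision rule depends on interval width, and the SAP does not mention confidence intervals for the arm difference. On that view this is a preference between two sound estimators. The validity point stands, and it is why the consequence is confined to precision. It does not remove the case for the extra estimate: the plan does test efficacy between arms, and a small trial gains most from using its baseline data well.

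Second, the size of the gain rests on assumed inputs. That also stands. Every reduction of 20% or more in the table needs a baseline SD 25% above the follow-up SD, which nothing in the documents supports. At k = 0.8 the gain is small or nil from rho 0.5 upward.

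Third, the programme is delivered in groups, and group-level variation arising at follow-up enters both estimators, so it dilutes the relative gain. Assuming groups of 8 and a group variance of 0.05 to 0.10 in the treated arm only, with equal SDs, the 12.5% at rho 0.5 falls to roughly 10.5% to 9%, and the 6.8% at rho 0.7 to roughly 5% to 4%. The gain shrinks but remains.

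Fourth, the SAP is written in the past tense, so a new model could look like a search for a better result. That is a fair warning. It is met by leaving the t-test in the lead and reporting the added estimate for every measure.

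**Conclusion.** The point holds. The lead psychosocial comparison has no covariate, and an ANCOVA on data already collected would generally estimate the arm effect more precisely. With similar SDs at the two times, the standard error falls by roughly 7% to 18% for correlations of 0.7 down to 0.3 at 26 per arm. The gain is small at 0.9, nil when the SD ratio is close to the correlation, and at worst a loss of about 1%.

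The direction follows from algebra and is secure. The size depends on a correlation and SDs that the documents do not give, and on independent participants. This is an improvement that should be made, not a fault that invalidates the planned test.

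**What to change.** Keep the change-score t-test as the pre-specified lead result. For each of the nine measures:

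- Add a regression of the time 2 score on arm and the baseline score of the same measure.
- Report the adjusted difference with its 95% CI.
- Fit the same model in the five imputed datasets and pool the results. State that the imputation model includes arm and the baseline score; the SAP does not describe that model.
- Label the estimate supplementary and specified after the protocol. The SAP is dated March 26, 2019, and randomisation ran from November 2016 to September 2017.
- Report it for all nine measures whatever it shows.

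The cost is one degree of freedom per model and a second, disclosed result for each outcome. No new data or participants are needed. The change does not deal with clustering from group delivery, multiplicity across outcomes, or informative dropout.

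### With five imputed datasets the intent-to-treat replicate is valid, but a borderline p-value depends noticeably on the random seed; rerun it with at least 50

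*SAP*

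**What the plan says.** Under Statistical Analyses, the SAP sets out two versions of the between-group comparison. The first is the available-data test: "We then used all available data to test between-group (intervention group versus wait-list control) differences in change scores from time 1 to time 2", by independent-samples t-test. The second is its replicate: "Using the intent-to-treat principle, we replicated the analysis using multiple imputation", with "five imputed datasets) to address missingness at time 2".

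The only figure that bears on the amount of missing data is in the feasibility sentence of the same section: "retention at time 2 (75% response". The software is named ("Analyses were conducted using IBM SPSS version 23"). The documents give no random seed, imputation model, reason for choosing five, check of Monte Carlo error, or significance level. Section VI of the protocol (Biostatistic Analysis) plans the t-tests and does not mention imputation.

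**The concern.** The replicate is there to show whether the available-data result survives once parents with missing time 2 scores are brought back in. That check is informative only if its answer comes from the data. With few imputations, part of the pooled estimate and much of its between-imputation variance are simulation noise. Near the significance threshold, agreement or disagreement between the two analyses can then come from the seed.

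The usual reassurance about five imputations is relative efficiency, 1/(1 + FMI/m), where FMI is the fraction of missing information and m the number of imputations. At FMI 0.25 this is 1/(1 + 0.25/5) = 0.95. It says that the pooled estimate loses little precision on average. It does not say how far one p-value moves when the imputation is rerun.

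Borderline results are plausible here. Section VI of the protocol lists three primary instruments, one of them a set of four visual analogue scales, and three secondary scales, all tested in about 70 parents. The SAP also says that the exploratory work is meant to support a larger trial, so which outcomes hold up after imputation may be carried forward.

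**Working it through.** The plan has no figure of its own to reproduce, because it gives no power calculation, significance level or Monte Carlo error.

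**Inputs**
- m = 5 (SAP, Statistical Analyses).
- About 70 parents (protocol, Recruitment: "A total of approximately 70 participants will be recruited for this study"), allocated 1:1 (SAP, Randomization), so about 35 per arm.
- FMI: not given. Assumed 0.25, because 75% retention would leave 25% missing at time 2. Range shown: 0.10 to 0.35.
- Two-sided 0.05: assumed. The protocol's primary hypothesis speaks only of "significantly greater scores on the primary outcomes".
- Pooling by Rubin's rules with large-sample degrees of freedom: assumed. The Barnard-Rubin degrees of freedom gave nearly the same ranges.

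**Step 1: Monte Carlo error of the pooled estimate.** In units of its standard error this is √(FMI/m).
- m = 5: √(0.25/5) = 0.22 (0.14 at FMI 0.10; 0.26 at FMI 0.35).
- m = 50: √(0.25/50) = 0.07.

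**Step 2: what that does to one p-value.** Scale the limiting total variance to 1, so that the within-imputation variance is U = 0.75 and the between-imputation variance is B = 0.25. A limiting p of 0.05 corresponds to an estimate of 1.96. With m = 5, and B estimated exactly:
- T = U + (1 + 1/m)B = 0.75 + 1.2 × 0.25 = 1.05, so the standard error is 1.025.
- λ = 0.30/1.05 = 0.286, and df = (m − 1)/λ² = 4/0.0816 = 49.
- Estimate at its centre: t = 1.96/1.025 = 1.91, p = 0.062.
- Estimate one Monte Carlo SD lower or higher (1.736 or 2.184): p = 0.097 or 0.038.

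The same calculation with m = 50 gives 0.051 at the centre, and 0.060 or 0.043 one SD either way. In practice B is itself estimated, on only m − 1 = 4 degrees of freedom when m = 5, which widens the spread further.

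**Step 3: full range over seeds.** Hold the observed data fixed, draw the pooled estimate from N(Q, B/m) and the between-imputation variance from B·χ²(m−1)/(m−1), and pool. The central 95% range for a limiting p of 0.05 is:

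| FMI (assumed) | m = 5 | m = 50 |
|---|---|---|
| 0.10 | 0.024–0.107 | 0.040–0.063 |
| 0.25 | 0.013–0.18 | 0.034–0.074 |
| 0.35 | 0.009–0.22 | 0.030–0.082 |

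The effect reaches a little beyond 0.05 itself. At FMI 0.25, a limiting p of 0.03 comes out at 0.05 or above in 34% of seeds with five imputations and 1% with 50. A limiting p of 0.07 falls below 0.05 in 24% and 4%.

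**Step 4: direct check.** Forty simulated trials (70 parents, 9 of 35 missing per arm, Bayesian linear-regression imputation) whose p-value at 5,000 imputations lay between 0.04 and 0.06 were each re-imputed 1,000 times at each m. The mean FMI was about 0.22. The average 95% range was 0.014–0.166 with five imputations and 0.032–0.069 with 50.

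**Step 5: how often it matters over all trials.** Steps 2 to 4 look only at results at or near the threshold. Drawing the limiting result at random as well, with FMI 0.25, the finite-m verdict at 0.05 differs from the limiting verdict as follows:

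| Situation | m = 5 | m = 50 |
|---|---|---|
| Null true | about 3% | about 1% |
| Limiting power 50% | about 10% | about 3% |
| Limiting power 80% | about 8% | about 2% |

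At FMI 0.10 the m = 5 figures are about 1.5%, 5% and 4%. Type I error with five imputations is about 0.05. Where limiting power is 80%, power is about 0.76 with five and about 0.80 with 50.

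**The case against.** The strongest reply is that five imputations is a legitimate choice. Rubin's variance includes the (1 + 1/m)B term and lowers the degrees of freedom, so the Monte Carlo noise is already charged to the interval. That stands: the test keeps its size and loses only about four percentage points of power. A reader might infer from the wide seed ranges that the intent-to-treat result is unsound. Neither the documents nor the calculation support that. What is weak is the reproducibility of one p-value, and only when it is borderline.

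A reader might also infer that a new seed would change the trial's conclusion. The documents do not support that either. The available-data t-test, which has no seed, comes first. The SAP calls the efficacy work preliminary and later refers back to its main preliminary efficacy analyses. Neither document ties a decision or a significance level to the imputed p-value.

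The amount of missing data is also uncertain. The 75% figure is a feasibility benchmark, not observed retention and not a stated tolerance for the efficacy analysis, and missing information need not equal the missing proportion. That stands too, which is why a range is shown. At FMI 0.10 the seed range with five imputations is narrower, but it still spans 0.05 widely (0.024–0.107).

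**Conclusion.** The point holds as one about reproducibility. If FMI is 0.25, a limiting p of 0.05 could be reported as anything from about 0.013 to 0.18 depending on the seed. Fifty imputations cut that to 0.034–0.074. Counted over all trials, the share of verdicts that differ from the limiting one falls from about 3% to 1% under the null, and from 8–10% to 2–3% at 50–80% power. Clear effects and clear nulls are little affected.

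These figures rest on the assumed FMI, a two-sided 0.05 threshold, Rubin's-rules pooling and a suitable imputation model. Seed noise weakens the replicate as a check on the available-data result, but this is a pilot with no decision rule attached. It is a cheap improvement.

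**What to change.** Rerun the multiple imputation with at least 50 datasets and a fixed, recorded seed. The SAP is written in the past tense and describes five datasets as already used, so the number should not simply be overwritten. Report the new result beside the five-dataset result and label it as a change from the stated plan. It would help to state the imputation model and the Monte Carlo error at the same time.

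The seed makes the result repeatable, and the larger number of datasets makes it stable. Some seed dependence remains at any finite number when the limiting p-value sits on the threshold: with 100 imputations the range at FMI 0.25 is still 0.038–0.066. The cost is negligible computing in the software already named, no new data, and a small amount of re-reporting.
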